Experts recommend a series of services and resources for a good functional recovery of patients who have suffered a stroke. Among other issues are training and health education programs. In this way, the nursing profession is trained to formulate personalized comprehensive care plans, promote comprehensive recovery, and strengthen communication with patients and their families. Nurses should perform interventions in accordance with general practice to provide continuity of care for stroke patients throughout the patient's recovery journey. Integrated care is desirable and constitutes a reference model for all situations considered. Planning for teaching and discharge from hospital can help families of patients who have suffered a stroke to make specific long-term arrangements for the expected functional outcome. In addition, post-discharge follow-up and support interventions should be implemented that are individualized to the caregiver's needs. Early rehabilitation intervention and evidence-based nursing interventions showed significant improvements in their scores on tests related to cognitive impairment and neurological deficit, as well as improved disability. However, there are hardly any standardized, approved and scientifically proven health education programs. The application of nursing interventions, through health education, to minimize the levels of depression caused by the disease, to two groups, case and control, will allow us to evaluate the influence of health education on the symptomatology of depression and improve the quality of life in patients who have suffered an ischemic stroke.

Study hypothesis

A nursing intervention based on health education will improve quality of life and reduce the symptoms of depression in patients who have suffered an ischemic stroke.

Objectives

General objective: to determine the effect of a nursing intervention based on health education on quality of life and depression symptoms in people who have suffered an ischemic stroke.

Specific objectives:

1. To assess and compare the level of depression in patients who have suffered an ischemic stroke.
2. To assess and compare the degree of autonomy and level of functional dependence of patients who have suffered an ischemic stroke.
3. To assess and compare the cognitive status of patients who have suffered an ischemic stroke.
4. To assess and compare neurological deficits of patients who have suffered an ischemic stroke.

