5. Assess and compare the risk of bronchoaspiration, the presence of pressure ulcers, swallowing, blood pressure, temperature and glucose level and assess the level of pain.
6. To correlate the cognitive state and the level of depression symptomatology with implemented variables.
7. To reduce the psychological impact of depression in patients who have suffered an ischemic stroke who have received health education.
8. To compare the level of depression symptoms in patients who have suffered an ischemic stroke who received health education with those who did not.

Type of study

It is a quasi-experimental, longitudinal and prospective clinical trial.

Material and methods

Scope of study

For the preparation of this study, the target population was patients who have suffered an ischemic stroke for the first time and were treated by physicians from the Neurology and Neurosurgery Service of the Lucus Augusti University Hospital (HULA).

Definition of the subjects to be studied

A representative sample size of patients who have suffered an ischemic stroke for the first time and treated by physicians from the Neurology and Neurosurgery Service of the HULA will be collected. From this sample, 2 groups will be extracted: the group to which a health education program will be applied and the control group to which this program will not be applied.

Subject selection and withdrawal

Inclusion criteria: anterior or posterior cerebral occlusion, age ≥ 18 years.

Exclusion criteria: intracranial hemorrhage, pregnancy, cognitive inability to participate, non-acceptance to participate in the study and administer questionnaires.

Recruitment and recruitment of participants

Prior to the recruitment process, the required informed consent signed by said participant will be obtained. Next, the variables will be collected. The recruitment of participants will be carried out by the principal investigator and collaborating researchers of the study in the neurology and neurosurgery ward:

- [name]
- [name]
- [name]
- [name]

The tasks "*Bibliographic Review, Study Design, Documentation Presentation, Database Design*" will be carried out by the collaborating researcher [name] supervised and in collaboration with the collaborating researchers [name] and [name].

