The recruitment of patients and immediate data will be carried out consecutively on the neurology and neurosurgery floor of the HULA by the collaborating researchers [name], [name], [name] and the principal investigator [name] and by the collaborating researcher in neurology consultation at the HULA [name].

The performance of the sessions is conditioned by the time of diagnosis of the stroke. In this way, it is necessary to recruit a minimum group of patients to carry out the workshops according to the established methodology. Subsequently, these will be carried out by the collaborating researcher [name]. After 3 and 6 months following the workshops, the same researcher together with the collaborating researcher [name] will carry out the follow-up and reevaluation in the neurology consultation of the HULA.

Finally, the process of integrating data and statistical analysis together with the final task of writing results, discussion and conclusions and their dissemination will be carried out by the collaborating researcher [name].

First, the initial evaluation of the patients will be carried out for the collection of variables to be studied in the neurology and neurosurgery floor of the HULA. Subsequently, recruitment will be carried out after delivering a sheet with all the information and the due consent document and they will be scheduled in outpatient clinics where the intervention of this study will be applied.

Assignment/Randomization Procedure

The procedure for assigning the members of each group will be random and the EPIDAT program will be used to make this selection.

Justification of the sample size

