According to the Atlas of Stroke in Galicia published by the Spanish Society of Neurology in 2018, the autonomous community of Galicia had a population of 2,701,819 inhabitants. Applying an incidence rate of 187.4 cases per 100,000 inhabitants, according to the IBERICTUS study, 5,064 new cases of stroke are estimated each year in Galicia per 100,000 inhabitants. The province of Lugo has 324,842 inhabitants on 1 January 2024, according to the INE, which, applying the same incidence rate, estimates 609 new cases of stroke per 100,000 inhabitants per year. Considering the proportion of ischemic strokes compared to other types of strokes 80:20, the estimated cases of the same would be 487 new cases in Lugo.

In relation to the calculation of the sample size, the following formula is applied.

$$n = \frac{\left[Z_{1-\frac{\alpha}{2}} \sqrt{2p(1-p)} + Z_{1-\beta} \sqrt{p_1(1-p_1) + p_2(1-p_2)} \right]^2}{(p_1 - p_2)^2}$$

Where:

- P2 (frequency of exposure between controls) = 0.4
- OR=4
- Assuming a 1:1 ratio of controls per case
- n = participants as the minimum sample size.

Assuming the calculations, the representative sample size of stroke patients in the province of Lugo would be 70 patients, 35 patients receiving the intervention and 35 controls.

Primary and secondary variables

Independent variables:

- Socioepidemiological: sex, age (< 65 years, 65-80 years, >80 years), date of ischemic event.
- Clinical Signs: type of stroke, treatment modality (received rt-PA or mechanical thrombectomy according to the candidates' protocol), number of falls, degree of pain, presence of pressure ulcers, genesis of new pressure ulcers, episodes of bronchoaspiration, presence of pneumonia, presence of dysphagia, vital signs (blood pressure, glycemia, temperature).
- You receive health education after a stroke or do not receive health education after a stroke.

Dependent variables:

- Assessment of cognitive status by scoring the Mini Mental State Examination (MMSE) questionnaire.
- Assessment of depression symptomatology by scoring on the Beck questionnaire (BDI) or also called depression self-report inventory.
- Assessment of autonomy and ability to perform in basic activities of daily living by means of a score from the Barthel Index.
- Neurological deficit using the NIHSS scale.
- Assessment of quality of life by scoring on the European Quality of Life Scale.

Instruments

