This section lists the instruments that will be used to measure the variables under study. They are described in a more extensive manner in Annex I.

1. Mini mental status examination (MMSE).
2. Beck Questionnaire (BDI).
3. Barthel index.
4. National institute of Health Stroke Scale (NIHSS).
5. Visual Analog Scale (VAS)
6. European Quality of Life Scale (EQLS).

Description of the intervention

The initial evaluation of the patients will be carried out for the collection of the variables to be studied upon admission. Subsequently, 2 groups will be established: the group to which a health education program will be applied (intervention of this study that will be specified below) and the control group. Finally, a follow-up is proposed at 3 and 6 months after the health education intervention to collect data related to the chronic/stabilization phase in post-stroke recovery.

Nursing intervention: Health education for post-stroke patients

Objectives

- Learn to identify and recognize prodromal symptoms of a new ischemic event.

- Identify what changes have occurred or may occur in patients after the sequelae of the ischemic event and how they may impact their daily lives.
- Describe the recommended care that patients can incorporate into their daily lives to reduce the impact of sequelae and improve their quality of life.
- Learn to recognize and manage early signs and symptoms of low mood and depressive symptoms.

Methodology

The sessions taught are based on meaningful learning, also supported by constructivist, cognitivist and behavioural learning.

The program consists of 3 fundamental pillars: session 1. *Early symptoms of stroke and recognition*, session 2. *Living with stroke: the day-to-day care*, session 3. *Mood management*. In addition, a workshop (session 4) will be designed for intervention in depression based on the development of coping tools through full breathing techniques, relaxation techniques, psychotherapy and mindfulness. All sessions will preferably be group. The contents of these sessions are detailed in Annex II.

Taking into account that 35 patients will receive the health education program, it is estimated that 3-4 groups of 8-12 people distributed independently in the sessions taught by the same instructor.

Materials

- Classroom for health education at HULA.
- Physical and digital support to support the sessions.

Time scheduling

The sessions will be divided into two different days.

Day 1 (40 minutes)

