Barthel Index: The Barthel Index or Maryland Disability Index was created in 1965 by Mahoney and Barthel. It is one of the most widely used instruments to determine functional capacity. It is a scale that assesses patients' independence in basic activities of daily living (ABVD). Its application takes between 2-5 minutes as a self-report and up to 20 minutes if it is carried out by direct observation. It assesses 10 ABVD, seven of which are activities related to personal care (eating, washing, dressing, grooming, bowel movements, urination, toilet use) and the other three have to do with mobility (ambulation, transferring, and going up/down stairs). Each activity is scored according to the degree of independence, with values ranging from 0 (total dependence) to 15 (total independence). The maximum score is 100, which would indicate that it is totally independent, while the minimum score is 0 and would indicate that the patient has total dependence. Its interpretation is as follows: 100 points independence, ≤ 60 mild dependence, 40-55 moderate dependence, 20-35 severe dependence and 5-20 total dependence.

Visual Analogue Scale (VAS): on the Visual Analogue Scale EVA, the intensity of pain is represented on a 10 cm line. At one end is the phrase "no pain" and at the opposite end "the worst pain imaginable". The distance in centimeters from the point of "no pain" to the one marked by the patient represents the intensity of the pain. It may or may not have marks every centimetre, although for some authors the presence of these marks decreases their accuracy. The way in which the patient is presented, whether horizontal or vertical, does not affect the outcome. It is the most widely used scale, even in critically ill patients. For some authors it has

advantages over others. The patient needs to have good motor and visual coordination, so it has limitations in the elderly patient and in the sedated patient. A value below 4 in VAS means mild or mild-moderate pain, a value between 4 and 6 implies the presence of moderate-severe pain, and a value greater than 6 implies the presence of very severe pain.

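### The researcher who teaches every workshop also helps to assess patients at 3 and 6 months, and no assessor is masked.

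*Protocol*

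**What the plan says.** The section on recruitment of participants gives the workshops to one collaborating researcher. It continues: "After 3 and 6 months following the workshops, the same researcher together with the collaborating researcher" will do the follow-up and re-evaluation in the neurology consultation. The section on timeline and expected completion date repeats this sentence, so it is not a slip in one place.

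The methodology of the intervention expects 3-4 groups, "distributed independently in the sessions taught by the same instructor". There is thus one teacher for the whole intervention arm. Controls receive nothing comparable; they are "the control group to which this program will not be applied".

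On the content of follow-up, the description of the intervention says only that "a follow-up is proposed at 3 and 6 months after the health education intervention to collect data related to the chronic/stabilization phase". It does not list the measures to be repeated. It places the initial evaluation before the two groups are established. Allocation is random, using EPIDAT. Nothing in the protocol masks an assessor or names an independent one.

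**The concern.** Randomisation makes the arms comparable at baseline. It does not protect a score that is given later by someone who knows the arm. Here the assessor not only knows the arm but taught the programme under test, and so has an understandable hope that it worked. A lenient score for an attendee, or a strict one for a control, would look like a treatment effect. Once the visits are done it could be neither detected nor corrected.

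What is at stake differs by outcome. The hypothesis is that "A nursing intervention based on health education will improve quality of life and reduce the symptoms of depression in patients", and both of those are patient-answered. The examiner-scored measures serve specific objectives 2 to 4 and part of objective 5 ("Assess and compare the risk of bronchoaspiration, the presence of pressure ulcers, swallowing"). The point therefore bears mainly on the secondary comparisons, with a weaker and unquantified effect on the main ones.

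**Working it through.** No figure in the protocol underlies this point, so the check is mainly a reading of who does what and which measures depend on the examiner.

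**1. Does the assessor know the arm?** One person teaches all groups, controls attend no session, and that person takes part in re-evaluation. Attendance alone therefore reveals the arm of every patient to that assessor. The second researcher may or may not know it; nothing keeps it from them.

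**2. Which measures depend on the assessor?** The dependent variables under primary and secondary variables, read with Annexes I and III:

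| Measure | Who produces the score | Exposure at follow-up |
|---|---|---|
| MMSE | Examiner awards the points (Annex III) | Yes, if repeated |
| NIHSS | Examiner grades each item | Yes, if repeated |
| Barthel Index | Either way: "Its application takes between 2-5 minutes as a self-report and up to 20 minutes if it is carried out by direct observation" | Only if observed |
| BDI | Patient: "Assessment of depression symptomatology by scoring on the Beck questionnaire (BDI) or also called depression self-report inventory" | Courtesy answers only |
| EQ-5D | Patient | Courtesy answers only |

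Two of five are examiner-rated, one depends on the mode of administration and two are patient-answered. Pressure ulcers and swallowing (objective 5) also need an examiner.

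**3. How many visits?** With 70 patients and two follow-ups, 70 × 2 = 140 visits are planned, of which 35 × 2 = 70 are of the instructor's own attendees. These counts assume no loss to follow-up. How the two researchers divide the scoring is not stated, so the number scored by the instructor is unknown and could be up to 140.

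**4. The 35 per arm.** The protocol's sample size reproduces. With OR = 4 and p2 = 0.4, p1 = 1.6/2.2 = 0.727. The stated formula at two-sided 0.05, with 80% power assumed because none is stated, gives 34.8, rounded up to 35. It enters below only as the number per arm.

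**5. Illustration of consequence.** Suppose there is no true effect and unmasked scoring shifts one arm by a net b standard deviations. The values of b are assumptions.

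- *t-test.* Noncentrality = b × √(35/2) = 4.18b, with 68 degrees of freedom, two-sided 0.05.
- *Pearson chi-square on a dichotomised score, no continuity correction.* Exact enumeration of two binomials with n = 35. Assumed control proportions are 0.2, 0.3, 0.4 and 0.5, and the proportion in the other arm is P(Z > z + b), where z is the control cut-off. For example, 0.4 becomes 0.325 at b = 0.2.

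| Assumed shift b | t-test | Chi-square (0.2 / 0.3 / 0.4 / 0.5) |
|---|---|---|
| 0 | 0.050 | 0.049 / 0.051 / 0.048 / 0.043 |
| 0.05 SD | 0.055 | 0.051 / 0.053 / 0.052 / 0.046 |
| 0.1 SD | 0.070 | 0.058 / 0.061 / 0.062 / 0.055 |
| 0.2 SD | 0.131 | 0.086 / 0.092 / 0.101 / 0.092 |

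The false-positive rate is about 5-7% for a shift of 0.1 SD or less and about 9-13% for 0.2 SD. This shows how the error rate responds to a shift. It is not evidence that a shift of that size would occur.

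**The case against.** The strongest reply concerns weight. The two outcomes in the hypothesis are patient-answered, and patients know their arm whoever assesses them. Objectives 2 to 5 speak of comparing without naming the arms. Most MMSE items are right or wrong, and on the Annex III form only the sentence and the drawing, one point each, carry written judgement criteria. The data notebook has no column labelled 3 or 6 months, so repetition of the MMSE or NIHSS is inferred from the word re-evaluation. A second researcher is present. The team is small and unfunded, its members have access to the study data under the ethical-legal section, and perhaps nobody on it can be masked.

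Part of this stands. The effect on the BDI and EQ-5D is limited, MMSE scoring leaves less room for judgement than NIHSS scoring, and the exposure holds only for measures that are repeated. The availability of a masked assessor cannot be settled from a document with names removed.

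The rest does not remove the point. The protocol lists MMSE, NIHSS and Barthel as dependent variables and receipt of health education as an independent variable, so comparing the arms on them is planned. A second assessor from whom nothing is withheld is not a masked assessor. The ethical-legal section limits who outside the team may see data; it does not require an assessor to see the allocation. Patients cannot be masked in an education trial, but assessors can.

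**Conclusion.** The concern holds. The overlap of instructor and assessor is certain on the text, stated twice, and no masking is provided. Who assesses patients is trial conduct that the protocol itself fixes, not something it leaves to an analysis plan.

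The reach is two of five dependent variables, a third if the Barthel Index is observed, and some objective 5 items, at follow-up only and as far as each is repeated. Baseline is unaffected because it precedes the formation of the groups. For the BDI and EQ-5D only courtesy answers to one's own instructor are at issue, and their effect cannot be quantified from the documents. The size of any bias is unknown, and the conclusion does not rest on the illustrative error rates. The change should be made because the bias is avoidable before follow-up starts and irreparable afterwards. It is not critical to the main hypothesis.

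**What to change.** In both places where follow-up is assigned (recruitment of participants, and timeline), replace the assignment with wording such as:

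> The researcher who teaches the sessions does not carry out the follow-up assessments. All re-evaluation measures planned at 3 and 6 months are done in both arms, in the same way, in the neurology consultation, by a team member who neither teaches nor handles allocation, has no access to the allocation list, and asks patients not to mention the sessions.

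The second researcher already assigned to follow-up can take this role if the sponsor confirms that this person can be masked. Otherwise another existing team member who meets the conditions should assess. The protocol should also state as a limitation that patients know their arm and may reveal it, so some response bias on the BDI and EQ-5D can remain.

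The change adds no instrument and no visit, and no staff provided that a current team member qualifies. Its cost is that one person carries the whole assessment load, at most 140 visits. For the second researcher that adds nothing if both were to see every patient, and about 70 visits if they had planned to share equally (an assumption). Where both would have seen each patient, the second rater is also lost.

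The wording does not settle when controls are seen. Follow-up is timed from the workshops, which controls do not attend, so their visit dates must be stated separately.

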This is a quasi-experimental, longitudinal and prospective clinical trial, which will be carried out in patients who have suffered an ischemic stroke and who were treated in the neurology unit of the Lucus Augusti University Hospital, where this same study will be carried out.

The main objective of the study is to determine the effect of a nursing intervention based on health education on quality of life and symptoms of depression in people who have suffered an ischemic stroke.

To achieve this objective, variables such as cognitive status, symptoms of depression, autonomy and ability to perform in basic activities of daily living, neurological deficit and quality of life will be assessed.

Regarding the total number of subjects under study, according to the Atlas of Stroke in Galicia published by the Spanish Society of Neurology in 2018, the autonomous community of Galicia had a population of 2,701,819 inhabitants. Applying an incidence rate of 187.4 cases per 100,000 inhabitants, according to the IBERICTUS study, 5,064 new cases of stroke are estimated each year in Galicia per 100,000 inhabitants. The province of Lugo has 324,842 inhabitants on 1 January 2024, according to the INE, which, applying the same incidence rate, estimates 609 new cases of stroke per 100,000 inhabitants per year. Considering the proportion of ischemic strokes compared to other types of strokes 80:20, the estimated cases of the same would be 487 new cases in Lugo. The representative sample size of stroke patients in the province of Lugo would be 70 patients, 35 patients receiving the intervention and 35 controls.

Términos MESH: Ischemic Stroke; Nursing; Depression; Anxiety; Health Education; Quality of Life

Background and justification of the project

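### The 35 per arm rests on a control-group exposure frequency of 0.4 that cannot hold in this design; the event and the power behind the figure are not stated

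*Protocol*

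**What the plan says.** In the Protocol, the section on the justification of the sample size prints the usual formula for comparing two proportions and lists its inputs: "P2 (frequency of exposure between controls) = 0.4", OR = 4, "Assuming a 1:1 ratio of controls per case" and "n = participants as the minimum sample size". It concludes that "the representative sample size of stroke patients in the province of Lugo would be 70 patients, 35 patients receiving the intervention and 35 controls". The formula contains a term for power, but neither this section nor any other gives power a value. The significance level, two-sided 0.05, appears only in the statistical analysis section.

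The design is described elsewhere. The section defining the subjects gives two groups: those who receive the health education programme, and "the control group to which this program will not be applied". The assignment section states that "The procedure for assigning the members of each group will be random", while the opening summary and the section on the type of study call the trial quasi-experimental. Receipt of health education is listed as an independent variable. All the dependent variables are scores (MMSE, BDI, Barthel, NIHSS, quality of life). The statistical analysis section plans a relative risk for the effect of the intervention and names no event. The hypothesis is that quality of life improves and depressive symptoms fall. Follow-up is at 3 and 6 months after the intervention.

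**The concern.** A frequency of exposure among controls, combined with an odds ratio, is an input for a study that compares how often two outcome groups were exposed in the past. Here exposure is set by the design: one arm gets the programme and the other does not. The share of controls exposed is therefore 0. The value 0.4 cannot be the quantity it is labelled as, whether the trial is called randomised or quasi-experimental.

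Once the label fails, nothing says what 0.4 is the frequency of. The odds ratio then has no event and no declared direction. A reader cannot tell which outcome the 70 patients are sized for, cannot judge whether 0.4 is plausible, and cannot set the planned relative risk beside a design value. With no stated power, the strength of the claim for 35 per arm is also unknown.

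**Working it through.** **Inputs.** P2 = 0.40, OR = 4 and 1:1 from the sample size section; two-sided alpha 0.05 from the statistical analysis section (z = 1.960). Power is not given, so 80%, 85% and 90% are tried (z = 0.842, 1.036, 1.282). The pooled p is taken as (p1 + p2)/2.

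**Step 1. The second proportion.** p1 = OR·p2 / (1 − p2 + OR·p2) = 1.6 / (0.6 + 1.6) = 0.727. Read as outcome risks, RR = 0.727/0.40 = 1.82.

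**Step 2. The protocol's own figure.**
- p = (0.727 + 0.40)/2 = 0.564; √[2p(1 − p)] = 0.701
- √[p1(1 − p1) + p2(1 − p2)] = √(0.198 + 0.240) = 0.662
- (p1 − p2)² = 0.327² = 0.107
- At 80% power: n = (1.960 × 0.701 + 0.842 × 0.662)² / 0.107 = 34.84, so **35 per arm**
- At 85%: 40 per arm. At 90%: 47 per arm.

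The stated size therefore reproduces at 80% power and not at the other two levels. Power at 35 per arm is 80.2%.

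**Step 3. Does the label fit?** The comparison divides the 70 by receipt of the programme. Controls do not receive it, so their exposure frequency is 0 against a stated 0.4. The figures make sense only as the risks of some event in the two arms.

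**Step 4. Which event?** With p1 as the intervention arm, OR = 4 makes the event more frequent with the programme.
- A favourable event fits: for example, good quality of life rising from 40% to 72.7%.
- Absence of depression also fits. By complement it means depression in 1 − 0.40 = 60% of controls against 1 − 0.727 = 27.3% with the programme (RR 0.45). The n is the same.
- Depression itself does not fit, because the hypothesis expects it to fall.

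**Step 5. Does the direction change the size?** Illustration only; this odds ratio is not in the document. Take 0.40 as the control risk of an unfavourable event and reverse the odds ratio to 1/4: p1 = 0.10 / (0.60 + 0.10) = 0.143, RR 0.36. The same formula gives n = 45.75, so 46 per arm, and 35 per arm has 68% power. The unnamed event can therefore move the size from 35 to 46 per arm.

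**Step 6. Completers.** For 0.40 against 0.727, 34 per arm gives 79.0% power. An assumed 30 completers per arm (5 of 35 lost, 14%) gives 74%. The document states no loss rate.

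**Step 7. Scores.** For a two-group comparison of means, 35 per arm detects about 0.68 SD at two-sided 0.05 with 80% power. This is context, not a correction.

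**The case against.** The strongest reply is that the formula is a sound two-proportion formula, that it returns 35, that two proportions suit the planned relative risk, and that the word exposure may be a carry-over from a software menu or a translation. Much of this stands. The arithmetic is right, and the basis can be kept once the inputs are named. A slip in wording would not, however, supply the event, its direction or the power. These belong to a justification that the Protocol itself sets out, so they are not matters left to a separate analysis plan.

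Several stronger readings are tempting and are not supported:
- **That a trial has no cases, so the ratio is also wrong.** The background section itself calls the two groups case and control. In that usage the ratio can simply mean 1:1 allocation, and it agrees with 35 and 35.
- **That the odds ratio has the wrong sign.** This holds only if the event is depression. The hypothesis also names quality of life, for which a rise is what is wanted.
- **That 0.4 is the depressed share of controls and the trial needs 46 per arm.** The background puts depressive symptoms in 20 to 50% of survivors, so 0.4 could be taken that way. But the document does not say so, and an odds ratio of 1/4 appears nowhere in it.
- **That losses make 70 too few.** The 74% rests on an assumed number of completers.

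It is also true that the 487 incident cases enter no term of the formula, so the description of the sample as representative does not follow from it. That has no effect on n and is a side point. Not giving a detectable difference on the scores is no error either, since the section sizes on proportions.

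**Conclusion.** The point holds as a fault in the basis of the sample size, not in its arithmetic and not as proof that 70 is too few. One stated input, 0.4, is impossible as labelled, because control exposure is 0 under the Protocol's own definition of the control group. The 35 per arm follows only if 0.40 and 0.727 are read as risks of an unnamed, favourable event, at two-sided 0.05 and an unstated 80% power. The size depends on what is missing: 40 or 47 per arm at 85% or 90% power, and 46 per arm at 80% power under the illustrative reversal of direction, where 35 would give 68%.

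The calculations assume the printed formula without continuity correction and the average of the two proportions as the pooled value. The reversed case and the 30 completers per arm are assumptions of this review. The point should be fixed before the result is read against the design; it does not by itself call for more patients.

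**What to change.** In the section on the justification of the sample size:

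1. Replace the exposure label and the OR with the control-arm and intervention-arm risks of a named event. Give its direction, the time point (3 or 6 months) and the source of both risks, and express the effect as the relative risk that the statistical analysis section plans.
2. Word the ratio as 1:1 allocation to the two arms.
3. State two-sided alpha 0.05 and the power that 35 per arm has for those risks, both for all 70 patients and for the number expected to complete 6 months. For 0.40 against 0.727 this would be 80% with 35 per arm and 74% with an assumed 30.
4. If the sponsor's event and risks do not give 80% with 35 per arm, restate the power; do not keep the present basis.
5. Optionally, add that 35 per arm detects about 0.68 SD on the scores with 80% power.

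The 0.40 against 0.143 case is an illustration and should not be written into the Protocol.

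The cost is one rewritten section, and the stated power may turn out less favourable than the 80% now implied.
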